#### **4.5.2 Data Safety Monitoring Board**

We will assemble a formal Data and Safety Monitoring Board (DSMB) for Phase II of this study to ensure that the safety of study subjects is protected and that the scientific goals of the study are being met. The assessment of feasibility in Phase I will help to determine what safety parameters are required for Phase II. The team assembled for the DSMB will have relevant and complementary expertise in adolescent psychiatry, clinical trial design, digital health, and statistics. Importantly, none of these individuals will be involved in any other capacity with this study or have any potential conflicts of interest in study-related outcomes.

The DSMB will review and evaluate information relevant to the safety of this study before the implementation of the protocol. Activities of the DSMB will include:

1. Reviewing the study protocol at the start of the study and any proposed amendments related to changes in study design, safety monitoring, or analytic plan.
2. Recommending alterations to the study design
3. Approving the study before commencement
4. Performing expedited monitoring of unexpected adverse device effects at the time of their occurrence and providing recommendations accordingly
5. Performing quarterly review of all clinical concerns
6. Performing ongoing quarterly review of study progress.
7. Reviewing any data that may reflect differences in safety between treatment groups
8. Determining whether study procedures should be changed or the study should be halted for reasons related to the safety of study subjects
9. Performing quarterly review of the completeness and validity of data to be used for analysis of safety and efficacy.

DSMB will convene by video- or teleconference prior to the start of the study and then quarterly through the study period. The Study PIs will be responsible for providing the study protocol to the DSMB prior to the initial meeting. At the initial meeting, the study PIs will meet with the DSMB to review the research protocol, informed consent documents, and plans for data safety and monitoring. The DSMB will review the protocol, discuss with the study team, discuss amongst themselves, and then make recommendations -if any- for modification of the protocol to the study team. The study team will record the recommendations and provide a written document to the DSMB following the meeting for approval and sign off.

The DSMB will then meet on a quarterly basis to assess study progress, data quality, participant recruitment, accrual, and retention, participant risks versus benefits, any breaches of confidentiality, clinical concerns, any interim results of safety and efficacy, and the ethics of this trial. Additional meetings may be convened when

deemed necessary. The study PIs will be responsible for providing a report to the DSMB prior to the meeting with all of the necessary information as outlined above.

The DSMB will provide verbal recommendations during the quarterly meetings related to continuation, termination, or other modifications of the trial and sign off on a written report following the meeting. The DSMB may also conduct independent analysis of the data. The Study PIs will be responsible for providing all data necessary to the DSMB to conduct this analysis. Unexpected serious device effects will be reported to the DSMB within 10 business days.

The IRB will receive a summary report of safety findings on an annual basis from the DSMB. This data and safety review as well as an assessment of protocol compliance and data quality will facilitate the early detection of safety signals and will maximize the likelihood of continued appropriateness of the research and protection of human subjects. The review will also ensure that participants who experience and report clinical concerns are provided with proper and, if necessary, ongoing attention. Any recommendations to improve patient safety, protocol adherence, or data quality will also be included.

## **5. Data Storage and Confidentiality**

Ethical guidelines for clinical research will be followed. All information obtained will be kept strictly confidential except as required by law and as otherwise indicated in this protocol and informed consent forms. We will comply with all mandated reporting rules. All researchers must demonstrate through training and testing up-to-date understanding of and commitment to follow all the guidelines and rules related to HIPAA, human subjects research, and good clinical practice that apply to this research.

Special care will be taken to prevent unauthorized access to data files. Limbix owned computers on which data files will be accessed will have password-protection. All study participants will be assigned participant ID numbers upon enrollment in the study and all subsequent data processing will be completed by reference to these numbers. The file linking participant ID number to personal identifying information, post-study interview audio recordings, and case report forms are stored on Google Drive with a business agreement in place protecting those files. Only research staff who require access for study-related activities have permissions to view and/or edit these files.

Signed electronic consent forms will be stored through HelloSign Part 11 compliant services.

The data generated by the Spark mobile client or web portal (used for baseline and post-intervention assessments for participants and parents) will be stored in an Aptible PostgreSQL database, which is backed up daily to geographically separate regions and encrypted at rest. After the study, the data will continue to be stored in said database. In the event that we need to decommission the database, we will move the data to cold storage in either Google Cloud Platform or Amazon Web Services (AWS) for the remaining length of time required to comply with GCP and will configure those buckets to be encrypted at rest as well. An anonymized copy of a portion of the study data will be synced daily to Google Cloud Platform for easier analysis. This copy of the data will have sensitive fields such as email, phone number, and first name removed and still require a valid Limbix employee login for access.

Access to the database requires SSH login to Aptible ephemeral containers that generate logs every time an employee logs in. Accounts on Aptible are limited on a need basis and employees are assigned to roles based

on the level of access they need to the system. The roles with access to the database are Account Owners and Enclave Owners only.

There will be a researcher portal where Limbix research staff can view aggregate and individual participant data of accounts that are enrolled in the study. Accounts on the researcher portal have access to study data limited by roles. The roles with access to study data are System Admin, Study Admin (PIs), Study Operator, and Read-only. All content on the researcher portal will require valid login credentials with password protection.

Data generated by the Spark mobile client or web portal will also be visible through an admin portal. Accounts on the admin portal will be limited to employees that need access in order to run and maintain technical infrastructure. All access to the admin portal will require valid login credentials with password as well as a one-time MFA password.

Anonymous usage data (such as button clicks and screen navigation) generated by the Spark mobile client will be aggregated using Google Analytics. All access to this data will require a valid Limbix employee login for access.

The Spark mobile application will also require valid login credentials with password protection to access individual account information. If the mobile app does not communicate with the server for 30 days, the user will be signed out of their account automatically and have to re-login to access their data in the mobile application. After participants have completed study participation, they will be marked as completed by a research staff member via the researcher portal and access to the mobile application will be restricted.

Only the study coordinator or PIs will directly contact study participants via phone or email per the study protocol to answer study-related questions. Text and email communication is encrypted in transit but unencrypted when being sent or received. Other research staff may interact with participants to troubleshoot software issues that may arise. Study clinicians may contact participants and/or parents (if under 18) if safety concerns arise.

The research coordinator will recommend that participants complete research-related activities including the virtual consent process in a private location. The research coordinator will conduct all research-related activities in a private room where individuals beyond the research investigators and staff cannot overhear the conversation. Participants are expected to complete the self-guided Spark program at a location of their choice.

No data with subject identifiers will be released, and all data obtained will be stored and maintained in a secure manner. All publications or reports of data will be anonymous in relation to subject identification. Protected health information will be disclosed to other professionals treating the patient only upon written authorization of the patient. Data will be stored in a confidential manner after the research is completed in accordance with GCP. The PI will retain responsibility for ensuring that data are maintained in a secure manner.

De-identified data or a limited data set may be shared for future research by Sponsor after a data use agreement is signed, where appropriate.

## **6. Transition from Research Participation**

N/A

## **7. Risk/Benefit Assessment**

### **7.1 Risk Category**

Minimal risk

### **7.2 Potential Risk**

Psychological risks: Some personal questions about life experiences or mood may bring up uncomfortable feelings.

Loss of confidentiality: As this study involves the use of identifiable, personal information, there is a chance that a loss of confidentiality will occur though steps to mitigate this risk have been taken as described below.

### **7.3 Protection Against Risk**

To minimize psychological risks, participants will be instructed that they can choose not to answer any question in any assessment and can discontinue their participation at any time. As the mobile app progresses in a linear fashion, questions in the mobile program must be answered to progress to the next task. During consent, participants will be informed that if they do not wish to answer a question in the mobile app they may discontinue their participation at any time. Patient responses to assessments completed weekly will be monitored as well as free response answers to questions delivered via the mobile app. This will enable detection of deterioration in clinical status. If such deterioration occurs, research staff will immediately contact the PI/study clinician. Participation will be terminated if clinical evidence indicates that continuing would not be in the best interest of the subject as determined by study PI in consultation with a study clinician. Weekly symptom reporting will also help the research team to identify any psychological or physical health consequences of study participation and, in consultation with study clinicians, determine the best way to mitigate further risks to participant health.

To minimize risks to privacy and/or confidentiality, only personnel with training in protecting private information about human subjects will have access to study data. Special care will be taken to prevent unauthorized access to data files.

Computers on which data files will be accessed will have password-protected access. All study participants will be assigned code numbers on entry to the study and all subsequent data processing will be completed by reference to these numbers. Special care will be taken to prevent unauthorized access to the data file connecting participant identity to subject numbers.

All publications or reports of data will be anonymous in relation to subject identification. Protected health information will be disclosed to other professionals treating the patient only upon written authorization of the patient. PIs will retain responsibility for ensuring that files are maintained in a secure manner during and after study.

Study personnel will ensure that no individuals outside the research team can overhear conversations during the virtual consent process. Participants in the study will be expected to complete mobile interventions at a location of their own discretion with respect to privacy and confidentiality.

Although every reasonable effort has been taken, confidentiality during Internet and phone-based communication procedures cannot be guaranteed and it is possible that additional information beyond that collected for research purposes may be captured and used by others not associated with this study.

Any data shared in the future will be stripped of all identifying information and protected health information or a limited data set may be shared with a data use agreement, when applicable.

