The virtual consent process will involve a video conference call during which the study coordinator will describe the research procedures, give the participant and their legal guardian (if required) time to review the consent form, and answer any questions they may have in accordance with good clinical practice (GCP) and human subjects research guidelines. Potential participants will be told that their participation is voluntary, that they are free to discontinue participation at any time, and that all information will be kept confidential with the exception of 1) mandatory limits to confidentiality and 2) safety concerns for participants or others. Participants will be told that they are free to refuse to answer any question during study interviews or questionnaires and that they can discontinue participation in the research at any time for any reason. All potential risks or discomforts will be explicitly listed and explained. Participants will be asked to notify the research team if changes to their treatment for depression or another mental health condition changes during the course of the study in order to determine if it is in the best interest of the participant to continue in this research. During consent, participants and their legal guardian (if required) will be asked to indicate whether they'd be interested in participating in a post-intervention interview about their experience with the program. Participants will also be asked to indicate whether or not they'd be willing to be contacted regarding future research opportunities. After all questions concerning any aspect of the study have been fully answered by study staff, a Part 11 compliant, electronic signature will be obtained from the participant or their legal guardian (if required) to document consent. Documentation of the assent of a minor will also be obtained. Participants or their legal guardian will be required to display a valid form of identification to verify identity. If the participant will turn 18 during the time period in which the participant will be engaging in research activities, and required consent from a legal guardian at the time of enrollment, a follow up consent appointment will be scheduled with the participant for them to consent as an adult of legal consenting age to continuing their participation in the study. If such consent cannot be obtained within a reasonable time frame, participation in the study will be terminated. Emancipated minors and/or minors who are financially independent will be allowed to provide informed consent without a legal guardian in accordance with federal guidelines, CA state regulations, and regulations of the state in which the minor resides.

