The research coordinator will direct participants and parents to a 21 CFR Part 11 compliant web portal where they will log in with their account credentials and complete baseline self-report assessments (see Assessments below). The research coordinator will send an email to the participant and their legal guardian (if required) with a safety plan document and instructions for completing and using this safety plan document should it be necessary. A reminder email to complete the safety plan will be sent to participants and their legal guardian (if required) 3 days later. The study coordinator will remain on the video call as participants and their legal guardian (if required) complete self-report assessments. After the study coordinator confirms that the assessments have been completed, the study coordinator will text or email the participant a link to download the study mobile app from the app store and will instruct them on how to download the Limbix mobile app. Participants will sign in using their login credentials, will undergo onboarding and be prompted to complete a baseline PHQ-8 in the mobile app. Completion of this initial PHQ-8 will be required for study participation to allow safety monitoring of symptom deterioration. Based on the randomization procedure, participants will have access to either the Limbix Spark intervention or the educational active control condition. The study coordinator will provide instructions on using the program to which the participant was assigned, answer any questions and end the video call.

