Both mobile programs (Limbix Spark and educational control) will be fully self-guided, completed by participants at home. Each program is designed to be completed over 5 weeks but users may progress through the program at their own pace. The Limbix Spark program progresses linearly, i.e., a task must be completed before a participant can progress to the next task. Content for a given week is not expected to take more than 60 minutes to complete. All participants will be prompted to complete a weekly PHQ-8 and clinical concerns questionnaire in the mobile app. Automated app notification reminders to complete these questionnaires will be sent. If users have not opened the app in 3 days, an automated app notification encouraging participants to use the app will be sent. An automated reminder notification will be sent 7 days before the end of the intervention period to remind participants that the intervention period will be ending in 7 days.

The legal guardian of participants under 18 will be emailed links to complete a parent-reported participant symptom check weekly. If they have not completed the questionnaire, they will be sent a reminder email 6 days later to remind them that the questionnaire is due the next day.

After the 5 week intervention period, participants and their legal guardian (if required) will be emailed links to complete post-intervention self-report assessments via secure web portal. Participants and their legal guardian (if required) will receive automated email reminders to complete the post-intervention assessments after 6 days if they have not completed the assessments. If participants or their legal guardian do not complete the post-intervention assessments within a week the research coordinator may reach out to participants or legal guardians via phone or email to encourage them to complete these assessments.

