## **8.2 Process of Consent**

Any trained member of the research team will be authorized to obtain informed consent.

Prior to participation, e-consent will be obtained for all participants over 18. For participants under 18, e-consent from a legal guardian and documented assent from participants will be obtained.

The consent process will be completed virtually via videoconferencing. To ensure participant privacy, the research staff member conducting the consent process will ensure that no one outside of the research team can overhear the consent process from their end and will recommend that the potential participant join the videoconference from a private location.

The researcher will explain the study, review the consent form, take time to answer any questions, provide time for decision-making and request an electronic signature.

The session will emphasize:

- 1) This is a research study testing an investigational medical device intended as a treatment for depression
- 2) Possible (minimal) risks and benefits of participation,
- 3) Participants can elect not to respond to any question(s) they are not comfortable answering
- 4) Participants can choose to end their participation at any time for any reason
- 5) All information will be kept confidential with the exception of certain information we must report for legal or ethical reasons including suspected child abuse or neglect, suspected elder abuse or neglect, or intent to harm oneself or others.

The consent and assent process will be considered complete only if the adolescent (and legal guardian if the participant is under 18) report comfort with and comprehension of all study procedures. The session will proceed only if informed consent is obtained.

After all questions concerning any aspect of the study have been fully answered by study staff, a Part 11 compliant, electronic signature (via HelloSign) will be obtained from the participant or their legal guardian (if under 18) to document consent. Documentation of the assent of a minor will also be obtained. Participants or their legal guardian will be required to display a valid form of identification to verify identity. Participants will be provided with a link to access and download a copy of the signed consent form at any time. Signed electronic consent forms will be stored through HelloSign Part 11 compliant services.

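### Consent tells participants they may decline any question, but app questions must be answered and leaving the study is the only alternative named, which can needlessly cost the week-5 PHQ-8

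*Combined protocol and SAP*

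**What the plan says.** **The freedom to decline** appears in three places, with different scope.
- Section 8.2, item 3 of the points the consent session will stress, has no exception: "Participants can elect not to respond to any question(s) they are not comfortable answering".
- Section 3.1 limits it to interviews and questionnaires: participants are "free to refuse to answer any question during study interviews or questionnaires".
- Section 7.3 limits it to assessments: "they can choose not to answer any question in any assessment and can discontinue their participation at any time".

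**The app rule** follows at once in Section 7.3: "questions in the mobile program must be answered to progress to the next task". The same section says participants will be informed during consent that "if they do not wish to answer a question in the mobile app they may discontinue their participation at any time".

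**The first in-app questionnaire** is compulsory under Section 3.1: "Completion of this initial PHQ-8 will be required for study participation". In the order of events there, this step comes after randomisation.

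**Linear progression** is stated for the active program in Section 3.1, "The Limbix Spark program progresses linearly, i.e., a task must be completed before a participant can progress to the next task", and again in Section 3.2. Neither control description (3.3.1, 3.3.2) mentions it.

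**The concern.** Item 3 in Section 8.2 does not fit Section 7.3 for questions inside the app. The consent script also joins two separate decisions: not wanting to answer a program question, and leaving the study. A participant who balks at one exercise is told of only one way out, and that way ends follow-up.

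The trial needs the opposite behaviour. An intention-to-treat comparison of PHQ-8 change to 5 weeks depends on people who stop using the app still giving the week-5 score. Any score lost through this wording is avoidable, because it comes from an instruction and not from a wish to leave. People who withdraw over personal mood questions may also differ in outcome from those who stay, so such losses need not be random.

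**Working it through.** No arithmetic applies. The documents give no rate of refusing app questions, overall or by arm. The check is whether each link from refusing a question to losing the score has text behind it.

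1. **Is the refusal promise unqualified anywhere?** Yes, in Section 8.2 item 3. The statements in 3.1 and 7.3 are narrower.
2. **Do the narrower promises still meet the app rule?** Yes, at the assessments delivered in the app. The weekly PHQ-8 and symptom check are completed there in both arms (Sections 3.1, 3.3.2, 3.4). They are questionnaires, so they may be declined under 3.1 and 7.3. They also sit in an app where 7.3 says questions must be answered to progress. The documents do not say which rule governs them. The initial in-app PHQ-8 is settled by 3.1, where it is compulsory, but item 3 of 8.2 does not mention that exception.
3. **What alternative is the participant told about?** Only discontinuing participation (7.3). No section tells the participant that stopping the app and staying in the study is possible.
4. **What follows from withdrawal?** Under the Phase II text of Section 3.1, a participant in either arm who withdraws during an intervention period loses the portal and the app together at that time.
5. **Where is the outcome collected?** Section 3.4 places post-intervention assessments in the web portal, and the schedule of assessments lists the PHQ-8 among them. The Phase II primary outcome (4.1) is PHQ-8 change from baseline to 5 weeks. With portal and app both closed, the plan has no route left to that score.
6. **What if the participant stalls but does not withdraw?** Section 3.1 closes access early only for withdrawal, loss to follow-up or being dropped. Someone who merely stops is still emailed the post-intervention links and paid for completing them whatever the adherence (3.1, 8.9). The week-5 score can still be obtained.
7. **What is kept after withdrawal?** Section 4.4 specifies mixed models on all available repeated measures, so weekly scores already recorded still contribute. What is lost is the week-5 value and any weekly scores after the exit.

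Steps 3 and 6 are the core of the point. The plan's procedures already allow stopping the app and staying in the study, but the script does not tell participants so.

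**The case against.** The strongest reply is that this is a small wording slip with its remedy already in the plan. Section 7.3 limits its own promise to assessments, states the app rule openly and has it disclosed at consent. Its wording on discontinuing is permissive, and nothing withdraws a person for stalling. Portal assessments, payment whatever the adherence, and a likelihood-based analysis limit the damage. The consent form itself is not in the reviewed text and may already make the distinction.

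Most of this stands, and it rules out four stronger readings.
- *That the refusal promise is untrue throughout.* Only item 3 of 8.2 is unqualified. The real overlap is item 3 against program questions, plus the in-app questionnaires.
- *That refusing a question means losing the primary outcome.* It does so only if the participant goes on to withdraw.
- *That the loss falls mainly on Spark.* The locking rule is stated explicitly only for Spark, but 7.3 speaks of the mobile app in general, no section says the control app is unlocked, and the compulsory first PHQ-8 and weekly questionnaires apply to both arms. Silence about the control app is not evidence of a difference.
- *That power or bias can be quantified.* The 27% attrition in Section 2.1 is one overall figure. Nothing shows that this cause adds to it, by how much, or in which arm. A bias figure based on completers would also not describe the planned mixed-model analysis.

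What the reply does not remove is that the script names one exit, and that exit closes the portal.

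**Conclusion.** The inconsistency is real and worth correcting as an inexpensive improvement. Section 8.2 item 3 conflicts with 7.3 and with the compulsory in-app PHQ-8 in 3.1. The discontinue sentence steers a reluctant participant towards withdrawal, and withdrawal ends collection of the week-5 PHQ-8, although the plan otherwise seeks outcomes whatever the adherence and analyses by intention to treat (4.4).

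The size is unknown and probably small. The conclusion assumes that some participants will take the script literally and withdraw when they could simply stop the app. Arm-related, informative loss is possible but not demonstrated. The point does not call the primary analysis or the sample size into question.

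**What to change.** 1. **Section 7.3 and the consent script.** Replace the sentence on discontinuing with, for example: *If you do not wish to answer a question in the program, you may stop using the program and remain in the study. You will still be asked to complete the post-intervention assessments in the web portal. You also remain free to leave the study entirely at any time.* The access rules in 3.1 already allow this and need no change.
2. **Section 8.2, item 3.** State the exceptions: program questions that must be answered to progress, and the initial in-app PHQ-8.
3. **Sections 3.1, 7.3 and 8.2.** Reconcile them on whether the weekly in-app PHQ-8 and symptom check, or single items in them, can be skipped. Say also whether someone who has stopped the program tasks is still asked to complete them.

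The new wording should not promise that program questions can be skipped, because the app as described does not allow it. Building a skip option into Version 3 is not needed for this point and would change a linear program between versions that are to be pooled.

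The cost is a short amendment to the protocol text and consent script. The app, the assessment schedule and the analysis do not change.
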